## ***Primary Endpoint***

The primary end point of the study is to measure ***overall survival*** defined as the time from randomization until death. In order to control for non-cancer death related factors that may compound the survival rate, a competing risk analysis rather than Kaplan-Meier will be used to compare the survival between the two groups.

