## **Data and Statistics**

Data will be evaluated according to intent to treat analysis. One- and two-year survival will be compared between two groups using competing risk analysis. This analysis will provide an estimate of HCC-related death in the presence of alternate yet plausible outcomes such as death from liver failure or liver transplantation. It is also a better technique in illustrating differential rates of competing outcomes in patients waiting for liver transplantation. This analysis will limit the effects of confounding factors such as death from liver disease. Secondary end points will be compared using Student's *t*-test for quantitative data and chi-squared ( $\chi^2$ ) test or Fisher's exact test for qualitative data. Demographics and standard of care laboratory data between groups will be compared. Logistic regression will be used to determine independent factors affecting survival.

The study is designed and powered to show at least 15% difference in mortality between two groups. Group size is calculated by assuming that patients in the TACE group will have at least 15% improvement in 2-year survival compared to the proton beam group. With 110 patients in each group the study has 80% power to detect a 15% difference in the mortality between two groups. We are not expecting any significant drop out because both treatments are considered crucial for patients' survival; and also based on our experience in treating these patients for many years at LLUMC. The level of significance is 0.05 (2-sided) for all statistical tests. The Statistical Package for the Social Sciences (SPSS 16.0 for window; SPSS, Inc., Chicago, Illinois) was used for all statistical analyses.

We will conduct an interim analysis after randomizing 40 patients in each group. This analysis will determine if there is any early significant difference in survival between two groups. The interim report will be submitted to the Institutional Review Board.

Data will be collected anonymously and subjects will be identified using a numerical code. The code will be stored at the PI and Co-PI office. The study database will be maintained and stored in the department of radiation medicine. Only PI, CO-PI and research coordinators will have access to the data.

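### The primary endpoint is death from any cause, but the only primary comparison specified is a competing-risk analysis of HCC-related death

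*Combined protocol and SAP*

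**What the plan says.** The Primary Endpoint section names overall survival, "defined as the time from randomization until death", with no limit on cause. The next sentence states its purpose, "In order to control for non-cancer death related factors that may compound the survival rate", and from that purpose it derives the method: "a competing risk analysis rather than Kaplan-Meier will be used to compare the survival between the two groups".

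The Data and Statistics section repeats that "One- and two-year survival will be compared between two groups using competing risk analysis". It then says what this yields: "an estimate of HCC-related death in the presence of alternate yet plausible outcomes such as death from liver failure or liver transplantation". It adds that the technique is better at "illustrating differential rates of competing outcomes in patients waiting for liver transplantation", and that "This analysis will limit the effects of confounding factors such as death from liver disease". The sample size in the same section is set on mortality, assuming that "patients in the TACE group will have at least 15% improvement in 2-year survival compared to the proton beam group", with 110 per group and 80% power at a two-sided 0.05 level.

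No log-rank, Cox or other all-cause comparison is named for the primary endpoint. The interim look and the logistic regression both refer to survival without a cause, but neither is the primary comparison. The Follow Up section ends research follow-up at death or transplant.

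**The concern.** The endpoint and the power statement refer to all deaths, while the analysis refers to one cause of death. These are different questions, and the plan treats them as one.

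The reason given for the switch does not hold. Death from liver disease occurs after randomization, so it cannot confound a randomized comparison; it is part of the outcome. The background sections list worsening liver function among the risks of both TACE and proton treatment. Excluding Child class C and MELD above 25 lowers the risk of liver death but does not remove it, since Child class B remains eligible. If one treatment kills more patients through liver failure, overall survival should show it. Under the plan those deaths could be displayed by arm as a competing outcome, but they would not be primary events.

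Stopping follow-up at transplant fits transplant as a competing outcome, but not an endpoint of time until death. Because downstaging can open access to transplant (Downstaging section), the number of patients leaving follow-up this way may differ by arm.

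**Working it through.** **What the text specifies.** Endpoint: death, any cause. Power: mortality. Event in the primary analysis: HCC-related death. Alternate outcomes: liver-failure death and transplant. One could read the plan as all-cause death with only transplant competing, but liver-failure death is itself listed among the alternate outcomes.

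**The plan's own figure.** No baseline rate is given, so 110 per group at 80% power cannot be confirmed. The pooled two-proportion formula is

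n = [1.96 √(2p̄(1−p̄)) + 0.842 √(p₁(1−p₁)+p₂(1−p₂))]² / (p₁−p₂)²

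At 2-year mortality of 12% vs 27%, p̄ = 0.195 and n = (1.098 + 0.463)² / 0.0225 = 108.3, so 109 per arm. Power at 110 is Φ[(0.15 − 0.1047)/0.0525] = 0.806. The mirror image, 73% vs 88% mortality, gives the same result.

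**Assumptions.** Constant hazards over 2 years; every death is either HCC or liver; transplant is ignored; HCC is 60% of deaths in the better arm; 110 per arm; two-sided 0.05. Three mortality pairs are used: 12% vs 27% (where 110 per arm gives about 80% power), 22% vs 37%, and 37% vs 52%. The last takes the 63% 2-year TACE survival cited in the TACE background section, from intermediate-stage patients, with TACE as the better arm as the sample-size text assumes.

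**Formulas.** Total hazard = −ln(1−mortality)/2. HCC incidence = (HCC hazard / total hazard) × all-cause mortality.

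For 12% vs 27%, the total hazards are 0.0639 and 0.1574, and the HCC hazard in the better arm is 0.6 × 0.0639 = 0.0384, giving 7.2% HCC death. In the worse arm:

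- Whole excess is liver death: HCC hazard stays 0.0384; 0.0384/0.1574 × 27% = 6.6%. Liver deaths are 4.8% × 110 = 5.3 vs 20.4% × 110 = 22.5.
- Half the excess hazard is liver death: 0.0384 + (0.1574 − 0.0639)/2 = 0.0851, giving 14.6%.
- All causes in proportion: 0.6 × 27% = 16.2%.
- Only HCC death differs: 0.1574 − 0.4 × 0.0639 = 0.1318, giving 22.6%.

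**Power at 110 per arm** (2-year HCC incidence in brackets):

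| Scenario | 12% vs 27% | 22% vs 37% | 37% vs 52% |
|---|---|---|---|
| All-cause death | 0.81 | 0.69 | 0.61 |
| HCC test, whole excess liver | 0.054 (7.2 vs 6.6%) | 0.059 (13.2 vs 11.9%) | 0.075 (22.2 vs 19.6%) |
| HCC test, half the excess liver | 0.42 (7.2 vs 14.6%) | 0.30 (13.2 vs 20.5%) | 0.22 (22.2 vs 29.3%) |
| HCC test, proportional | 0.55 (7.2 vs 16.2%) | 0.42 (13.2 vs 22.2%) | 0.33 (22.2 vs 31.2%) |
| HCC test, only HCC differs | 0.90 (7.2 vs 22.6%) | 0.825 (13.2 vs 29.0%) | 0.77 (22.2 vs 38.9%) |

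In the whole-excess-liver row, liver deaths are about 5 vs 22, 10 vs 28 and 16 vs 36 patients. With HCC shares of 40% to 80%, that row stays between 0.05 and 0.09.

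**Direction.** In that row a cumulative-incidence comparison makes HCC death look 0.6 to 2.6 points lower in the arm with more deaths, because patients who die of liver failure cannot later die of HCC. In simulation, a cause-specific log-rank test showed no such tilt (significant about 5% of the time, split evenly). The plan does not say which test it means.

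**Transplant.** In the cited proton-only phase II study, 6 of 34 patients (17.6%) were transplanted. If that applied to both arms, 0.176 × 220 ≈ 39 patients would leave follow-up at transplant; at 10% to 30%, 22 to 66. The resulting bias cannot be estimated from the documents.

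**The case against.** The strongest reply is that the plan contradicts itself and is not plainly wrong: it says survival will be compared, names no test, and offers the HCC-death estimate as one output of the technique. It is true that no test is named. But the only event the text gives for the analysis is HCC-related death, and its stated purpose is to control for non-cancer death. No all-cause comparison can be recovered from it.

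A second reply is that the worst case is true by construction: if HCC hazards are set equal, an HCC test must be significant about 5% of the time. That is correct. The case shows what the test cannot see; it does not predict what will happen, and the documents do not say how likely so large a liver-death difference is. The direction of the power change is also unknown, since power rises if only HCC death differs. What stands is that the stated 80% does not carry over to HCC death in either direction.

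A third reply is that renaming the endpoint HCC-related death and re-powering would also remove the contradiction. It would, but it would change the question and the basis of the sample size. Making the analysis all-cause follows the endpoint and power the plan already states.

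Finally, all-cause power is itself only 69% or 61% in two of the three scenarios. That comes from the missing baseline rate, a separate matter that this change neither causes nor resolves.

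**Conclusion.** The concern holds, and it must be fixed before outcomes are known, because choosing between two primary analyses afterwards would compromise the main conclusion. The conclusion rests on the text and needs no assumed rate: as written, the primary comparison does not address overall survival. To the extent that a survival difference comes from liver-failure deaths, the primary test would not register it, even if those deaths are tabulated.

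The numerical size is illustrative. Across the three assumed mortality pairs, with a 60% HCC share in the better arm, the HCC test has anywhere from 5% to 90% power where the all-cause test has 61% to 81%, depending on which causes differ. Ending follow-up at transplant adds an unquantified loss of deaths.

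**What to change.** - **Primary Endpoint and Data and Statistics:** make the primary analysis death from any cause by intention to treat, with a standard survival comparison (for example Kaplan-Meier estimates at 1 and 2 years and a log-rank test). State that the power refers to all-cause death.
- **Competing-risk analysis:** keep the cumulative incidence of HCC death, liver-failure death and transplant, by arm, as supportive. It needs a stated rule for assigning cause of death, which the plan lacks.
- **Data and Statistics:** delete the sentence that calls death from liver disease a confounding factor.
- **Follow Up:** continue alive/dead follow-up after transplant so that later deaths count. Use censoring at transplant, or transplant as a competing event for all-cause death, only as sensitivity analyses, because treatment may change access to transplant through downstaging.

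The cost is rewording of three sections, a cause-of-death rule, and periodic vital-status checks on transplanted patients (about 39 of 220 if the 18% applied to both arms; 22 to 66 at 10% to 30%, all assumed). It needs no study imaging or laboratory tests, and the change itself does not alter the sample size.

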## **Transarterial Chemoembolization (TACE)**

Multiple studies have shown contradictory results regarding the efficacy of TACE in improving survival compared to other treatments. The majority of these studies are retrospective studies or used a small sample of patients. These contradictory results have been attributed to the difference in endpoints of these studies and the multiple variables such as tumor size and liver function that usually impact and confound the outcome.

In one large study involving several institutions in Italy, chemoembolization did not improve survival compared to supportive care only. Patients who did not undergo TACE lived as long as patients who received TACE, even though the tumors were more likely to shrink in size in patients who were treated (8). Llovet et al. used TACE as a palliative treatment in a prospective, randomized controlled trial published in 2002 on 112 patients with intermediate stage HCC not felt to be candidates for other therapies. The patients randomized to TACE versus supportive care only. A significant increase in survival for the chemoembolization group was observed when compared with control (82% and 63%, 1-and 2-year survival, respectively, compared with 63% and 27%) (9). A study in Japan has shown that TACE can downstage liver cancer (10). Downstaging created the option for transplant in some of these patients. Otherwise, these patients had tumors that were not operable (eligible for operation) or not qualified for liver transplantation because of the initial large size of their tumors (10). More importantly, this study showed an improvement in survival in patients whose tumors became considerably smaller. In the U.S., trials are underway to see whether doing TACE before liver transplantation increases patient survival as compared to liver transplantation without TACE. Risk and common side effects of TACE include: bleeding, infection, worsening liver function, perforation of the common bile duct, veins or arteries, abdominal pain, nausea, vomiting, and fever.

It is reasonable to conclude that TACE is a procedure with acceptable side effects and a controversial small advantage in improving survival, especially in patients with small tumor and for patients waiting for liver transplantation. TACE can be used only in patients with relatively preserved liver function. The reason for this is that these procedures, as mentioned previously, can lead to liver failure in individuals with poor liver function.

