## **Proton Beam Radiotherapy**

Proton beam radiotherapy has physical properties that target the actual tumor mass and spare large portions of nearby normal tissues. Phase I and II trials demonstrated the safety of this treatment modality in decompensated patients with cirrhosis with HCC. Few trials in Southeast Asia and the United States demonstrated that proton beam could be an effective treatment that may improve survival and control tumor progression. Tokuyue et al. treated 79 patients who had HCC with proton beam radiotherapy (12). A median total dose of 72 Cobalt gray equivalents in 16 fractions was delivered. At 5 years, local tumor control and survival rates were 89% and 27% respectively. Kawashima et al. used the same fractionation scheme in 30 patients with HCC with an indocyanine green retention rate at 15 minutes. Complete disappearance of tumors occurred in 24 patients (80%). The 2-year local regression-free rate in that study was 96%, and the 1-year and 3-year survival rates were 77% and 62% respectively (13). Eight patients developed hepatic insufficiency, which presented as ascites, elevated transaminase levels, and/or asterixis from 1 to 4 months after therapy (13). Bush et al., in a phase II trial where 34 patients with HCC completed 15 sessions of total 63 cobalt Gray equivalents, 75% local tumor control rate and overall survival rate of 55%. Six patients underwent liver transplantation 6 to 18 months after proton therapy. In 2 patients, there was no evidence of tumor pathology, demonstrating that proton therapy can eradicate HCC (14). A complete pathologic response was also observed by Merle et al (15). Risks involved in proton treatment include internal bleeding, radiation hepatitis (elevation in liver enzymes), worsening liver function (elevation in

bilirubin and INR) and perforation of the surrounding solid organ such as small bowel and stomach.

Proton beam radiotherapy has been associated with some of the best outcomes in HCC patients; however, further studies are needed to compare proton to other treatments.

In this randomized trial we wish to compare head-to-head the efficacy of proton beam radiotherapy versus TACE in treating patients with unresectable HCC.

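### Coded cause of death decides the competing-risk comparison, yet no coding rule, assessor or masking is specified; if coding differs by arm, the false-positive risk rises

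*Combined protocol and SAP*

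**What the plan says.** The Primary Endpoint section names overall survival, "defined as the time from randomization until death". It then says that "a competing risk analysis rather than Kaplan-Meier will be used to compare the survival between the two groups", and gives the reason: "In order to control for non-cancer death related factors". Data and Statistics describes the output as "an estimate of HCC-related death in the presence of alternate yet plausible outcomes such as death from liver failure" (transplantation is named as a further such outcome) and adds: "This analysis will limit the effects of confounding factors such as death from liver disease". The cause assigned to a death therefore decides whether it counts as the event or as a competing outcome.

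The background sections connect liver failure with both treatments. Of TACE-type procedures the protocol says they "can lead to liver failure in individuals with poor liver function". Of a 30-patient proton series it says: "Eight patients developed hepatic insufficiency". Worsening liver function is also among the listed risks of proton treatment.

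No section defines an HCC-related or a liver-failure death, says which records decide the cause, names who decides, or mentions masking. Independent review is specified only for confirming the HCC diagnosis (Study Design) and measuring lesions (Secondary Endpoints). No analysis that ignores cause of death is planned.

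**The concern.** Every patient has both cirrhosis and HCC, so a terminal decline can often be attributed to either. A catheter procedure and 15 proton sessions cannot be mistaken for each other, so whoever assigns the cause will probably know the arm unless steps are taken. Information may also differ by arm: under Follow Up, only proton patients are additionally seen by their radiation oncologist, every 3 months in the first year and every 6 months after that.

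If the same decline is called tumour death after one treatment and liver failure after the other, deaths move into or out of the event count by arm. That can produce an apparent difference between equal treatments or hide a real one. Because either treatment may itself contribute to liver failure, the deaths set aside as competing outcomes may include treatment effects.

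**Working it through.** **Inputs from the documents.** 110 per arm, 1:1 allocation, two-sided 0.05 (Methods; Data and Statistics).

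**Two-year mortality, q (assumed; the plan gives no base rate).**
- 12%: the plan states 80% power for a 15% difference. Read as percentage points, 110 per arm gives 80.6% for 12% v 27% (109 per arm needed for 80%), or about 80% for the mirror image near 73% v 88%.
- 37%: 1 − 0.63, from the two-year TACE survival of 63% cited in the TACE section. At 37% v 52% power would be 61%, with 172 per arm needed, so this is not the rate behind the stated power.
- 25%: a value between the two.

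**Other assumptions.** Share of deaths that are HCC-related, s = 60% (varied below); the rest are liver failure. Miscoded fraction m = 20%. Full two-year follow-up, no transplants, no other causes of death. The test is a pooled two-proportion z test on coded HCC deaths at two years, a simplification of a cumulative-incidence comparison.

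**Formulas.** True HCC death h = q·s and liver-failure death l = q·(1 − s), equal in both arms.
- One-way miscoding: h(1 − m) v h.
- Two-way miscoding: h(1 − m) v h + m·l.

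At q = 37%: h = 0.37 × 0.6 = 0.222 and l = 0.148. One-way: 0.8 × 0.222 = 0.178 v 0.222. Two-way: 0.178 v 0.222 + 0.2 × 0.148 = 0.252.

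| Mortality | HCC deaths per arm | Recoded, one-way | One-way rates | False positives | Two-way rates | False positives |
|---|---|---|---|---|---|---|
| 12% | 7.9 | 1.6 | 5.8% v 7.2% | 7% | 5.8% v 8.2% | 11% |
| 25% | 16.5 | 3.3 | 12.0% v 15.0% | 10% | 12.0% v 17.0% | 19% |
| 37% | 24.4 | 4.9 | 17.8% v 22.2% | 13% | 17.8% v 25.2% | 26% |

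With no miscoding the rate is about 5% in each row. At 30% one-way miscoding it is 10%, 17% and 24%.

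**Varying the HCC share from 40% to 75%.** At 25% and 37% mortality, one-way 20% miscoding gives 9% to 16% and two-way 20% gives 16% to 33%.

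**Controls.** Miscoding 20% of HCC deaths equally in both arms leaves the rate at about 5% (4.5% to 5.3% for mortality of 12% to 37%). Testing all-cause death gives 5.0% at 25% mortality and 5.1% at 37%.

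**How many recodings reach p < 0.05?** Start from 24 v 24 HCC deaths.
- Recode 5 in one arm (24 v 19): difference 5/110 = 0.0455; pooled rate 43/220 = 0.1955; standard error √(0.1955 × 0.8045 × 2/110) = 0.0535; z = 0.85.
- Recode 10 (24 v 14): z = 1.78. Recode 11 (24 v 13): z = 1.98.

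So 11 of 24 are needed in one arm, or 7 in each arm in opposite directions. For 10 to 40 HCC deaths per arm the one-way number runs from 7 to 14. If chance has already left a gap, few suffice: 28 v 18 has z = 1.66, and two further recodings (28 v 16) give z = 2.02.

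**The case against.** **Silence is not a rule.** A reader might infer that the plan hands coding to clinicians who know the arm. The documents do not say so; they do not say who codes or how. The supportable statement is that rule, assessor and masking are unspecified.

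**Arm-dependence is not shown.** The background sections say both treatments can harm the liver, which fits similar miscoding in both arms at least as well, and that leaves the error rate near 5%. The largest figures need opposite miscoding in the two arms, for which the documents give no mechanism. This stands: the inflation is conditional. Visibly different treatments and unequal follow-up make differential coding possible, not established.

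**A few recodings do not manufacture a result.** It is tempting to say that a handful of arm-dependent codings can create a false finding. From balance they cannot; they raise the risk, or tip a comparison already close to significance.

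**37% may be too high.** The cited TACE trial enrolled intermediate-stage patients not thought suitable for other therapies. This trial requires San Francisco criteria and excludes Child class C and AFP above 500. The objection is fair, and is why lower rates are shown.

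**The point derives from the endpoint mismatch.** Survival is defined as time to any death and the power is stated for mortality; analysing that endpoint would remove coding from the primary comparison. That is right, and it shapes the fix. Any cause-specific result still reported would remain exposed.

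**Conclusion.** The concern holds in conditional form. As written, the main comparison depends on a boundary between HCC death and liver-failure death that the plan neither defines nor protects. If 20% of one arm's HCC deaths crossed it, the false-positive rate would be about 7% to 13% instead of 5%; with opposite 20% miscoding in the two arms, about 11% to 26%. These ranges cover assumed mortality of 12% to 37% with 60% of deaths HCC-related. The miscoding fractions and HCC share are assumptions without a source in the documents, and transplantation and other causes of death are left out. The documents support neither a claim that bias will occur nor its direction. A change before outcomes are seen is still justified, because an analysis free of this boundary is cheap and matches the endpoint as defined.

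**What to change.** In Data and Statistics, before the interim look planned after 40 patients per group, pre-specify two analyses that do not depend on the boundary: all-cause death, which is the endpoint as the Primary Endpoint section defines it, and HCC plus liver-failure death as a single event. State that any cause-specific conclusion is to be read alongside them.

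If the cause-specific result is kept:
- write the cause-of-death rule before any outcome is seen;
- apply it from existing records with treatment removed;
- include a category for deaths with neither documented progression nor decompensation;
- do not let the rule rest on unmasked progression reads alone. Secondary Endpoints judges progression by arterial enhancement, Appendix 3 has TACE embolize the artery feeding the tumour, and the radiologists are not said to be masked. Removing treatment from the record afterwards would not undo a difference that entered at the reading.

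The cost is one or two extra analyses and a short written rule; no new tests or adjudication panel are needed. A fixed rule will still misclassify some deaths. The aim is that such errors do not depend on arm.

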## ***Secondary Endpoints***

### **1. Time to progression.**

This endpoint reflects the time between randomization and radiological progression as defined by the amendments of the Response Evaluation Criteria in Solid Tumors (RECIST) (16).

**A. Complete Response** is defined as the disappearance of any intratumoral arterial enhancement in all target lesions.

- B. Partial Response** is at least a 30% decrease in the sum of diameters of viable (contrast enhancement in the arterial phase) target lesions, taking as reference the baseline sum of the diameters of target lesions.
- C. Progressive Disease** is an increase of at least 20% in the sum diameters of viable (enhancing) target lesions, taking as reference the smallest sum of the diameters of viable (enhancing) target lesions recorded since the treatment started. Or the appearance of one or more new lesions.

A newly detected hepatic nodule will be classified as HCC- and will be declared as evidence of progression- when its longest diameter is at least 10 mm and the nodule shows the typical vascular pattern of HCC on dynamic imaging. Lesions larger than 10 mm that do not show a typical vascular pattern can be diagnosed as HCC by evidence of at least 1 cm interval growth in subsequent scans.

- D. Stable Disease** is any cases that do not qualify for either partial response or progression disease.

MRI or CT-scan of the abdomen will be used to determine the targeted lesions for treatment and its baseline measurements. Target lesions will be measured using a single linear summation of the large diameter of the tumor. The average of two measurements by two independent radiologists will be considered for baseline and follow up assessment.

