## **2. Downstaging**

This endpoint will be applied to subjects in whom their tumor burden exceed Milan criteria but meet San Francisco criteria (Appendix 1). The direct measurement of the longest diameter of the viable tumor will be compared pre-and-post treatment. Usually, patients with San Francisco criteria will not be qualified for MELD score exception upgrade on UNOS waiting list unless their tumor burden is down-staged to Milan criteria using one of the locoregional treatments. Measuring this endpoint will help in comparing the efficacy of proton versus TACE in downstaging tumor in patients who meet San Francisco criteria.

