## ***Follow Up***

Patients with HCC usually require either CT scan or MRI of the abdomen to be performed routinely every three months to monitor tumor progression. Patients undergoing any locoregional treatment usually require a CT scan or MRI of the abdomen to be performed 4-6 weeks after the treatment and then every three months. Follow up imaging will be the same modality used at baseline (CT or MRI). Patients are usually evaluated in the liver clinic 4 weeks after treatment and then every three months. Subjects receiving proton therapy will also be followed in radiation medicine clinic by their treating radiation oncologist every 3 months for the first year then every 6 months. Participants in this study will be followed according to this protocol. No radiological testing will be ordered for the purpose of the study as the recommended assessments follow the current standard of care. Patients will be followed for research purposes until death or transplant, or until which time the study investigators determine the study is complete.

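### Time to progression is left to Student's t-test, with no time-to-event method and no censoring rule

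*Combined protocol and SAP*

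**What the plan says.** Secondary Endpoints, item 1, defines time to progression as a duration: "This endpoint reflects the time between randomization and radiological progression". It names no fixed time point and gives no rule for a patient who has not progressed.

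Data and Statistics assigns tests by data type: "Secondary end points will be compared using Student's" t-test or a test for proportions. The t-test is the "test for quantitative data and chi-squared" or Fisher's exact test covers qualitative data. The competing-risk method is tied to survival, both under Primary Endpoint and in Data and Statistics: "One- and two-year survival will be compared between two groups using competing risk analysis". No section gives a log-rank test, Cox model, cumulative incidence or censoring rule for progression.

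Follow Up sets when observation stops: "Patients will be followed for research purposes until death or transplant, or until which time the study investigators determine the study is complete". That is a follow-up rule. It does not say how a patient whose follow-up stops without progression enters the analysis.

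For factors affecting survival the plan says: "Logistic regression will be used to determine independent factors affecting survival".

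**The concern.** A duration is quantitative, so the stated rule sends time to progression to the t-test. If that was not intended, the endpoint has no method at all. The same rule suits the other secondary measures, such as tumour response and the downstaging comparison ("The direct measurement of the longest diameter of the viable tumor will be compared pre-and-post treatment"). It does not suit an endpoint that some patients will not reach while under observation.

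A t-test needs a number for every patient. The analyst must drop non-progressors, which sits badly with the intent-to-treat statement in the same section, or enter their exit time as if it were progression. The plan does not choose, so the choice could be made after the data are seen. Analysing progression as yes/no by chi-squared also ignores time and censoring.

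Incomplete times are likely. In the phase II proton trial cited in the background, in which 34 patients completed treatment, "Six patients underwent liver transplantation 6 to 18 months after proton therapy": 6/34 = 18%. Transplant is also a treatment goal in this population, so it could differ by arm. The trial could then miss a real delay in progression or report one that does not exist.

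**Working it through.** The plan states no power or event rate for time to progression, so there is no figure of its own to reproduce. Its 110 per group and 80% power concern mortality; only the 110, the 1:1 allocation and the two-sided 0.05 level are used here.

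**Assumptions (not in the documents).** Exponential progression times; transplant or death exponential and independent of progression; observation capped at 24 months. Let p be the 24-month probability of transplant or death acting alone. Then λ = ln 2/median, μ = −ln(1−p)/24, Λ = λ + μ and S = exp(−24Λ).

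- Progressing by 24 months: (λ/Λ)(1−S). Leaving first: (μ/Λ)(1−S).
- Mean of all observed times: (1−S)/Λ, with second moment 2[1−S(1+24Λ)]/Λ².
- Mean among progressors: 1/Λ − 24S/(1−S), with variance 1/Λ² − 24²S/(1−S)².
- Log-rank power: Φ(|ln HR|·√(D/4) − 1.96), where D is the number of progressions.

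Both means depend only on Λ, the total rate of leaving observation. The t-test therefore cannot separate progression from transplant or death.

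**Equal exit, medians 12 v 18, p = 30% in each arm.** λ = 0.05776 and 0.03851; μ = 0.01486; Λ = 0.07262 and 0.05337.

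- Leaving first: 17% and 20%, close to 6/34. Progressing: 65.6% and 52.1%.
- Log-rank: D = 110 × (0.656 + 0.521) = 129.5. z = 0.4055 × √32.4 = 2.31, power Φ(0.35) = 64%.
- t-test, all times: means 11.36 and 13.53, difference 2.17. SDs 8.25 and 8.61 give SE 1.14, z = 1.91, power about 48%.
- t-test, progressors only: means 8.68 and 9.51, difference 0.83. SDs 6.44 and 6.66 give SE 1.16, z = 0.71, power about 11%.

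The true difference in means is 18/ln 2 − 12/ln 2 = 8.7 months.

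**Masking, medians 12 v 18, p = 20% v 50% (higher in the slower-progressing arm).** Λ = 0.05776 + 0.00930 = 0.06706 and 0.03851 + 0.02888 = 0.06739. Mean observed times are 11.93 and 11.89, and among progressors 8.91 and 8.90. The benefit vanishes.

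**False difference, median 12 in both arms, p = 20% v 50%.** Λ = 0.06706 and 0.08664. Mean observed times are 11.93 and 10.10, a spurious 1.8 months.

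**Simulation (5,000 trials per scenario), percentage of trials rejecting:**

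| Scenario | Log-rank | t, progressors only | t, all times | Chi-squared yes/no |
|---|---|---|---|---|
| 12 v 18, 0% each | 69 | 12 | 63 | 65 |
| 12 v 18, 30% each | 64 | 11 | 47 | 52 |
| 12 v 18, 50% each | 59 | 10 | 37 | 48 |
| No difference, 30% v 30% | about 5 | about 5 | about 5 | about 5 |
| No difference, 20% v 30% | 5-6 | 5-6 | 8-10 | 7-8 |
| No difference, 20% v 40% | 5-6 | 7 | 19-27 | 14-19 |
| No difference, 20% v 50% | 5-6 | 10-12 | 38-55 | 26-38 |
| 12 v 18, 20% v 30% | 64 | 9 | 28 | – |
| 12 v 18, 20% v 50% | 62 | 5 | 5 | – |

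Rows with no difference cover a median of 12 or 18 months in both arms.

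**A second set of assumptions** (36 months' accrual, 24 months' minimum follow-up, reference median 8-18 months, median time to death or transplant 18-36 months and equal by arm) gives, at HR 0.60, log-rank power of 68-90% against 12-53% (progressors only) and 36-80% (all times).

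**Lesser point, logistic regression.** It needs survival status at a fixed time. With 220 patients, 63% two-year survival (the TACE figure in the cited 2002 trial), a binary factor with HR 1.6 and 30% transplant, two-year status is unknown in 23%. Power is 55%, against 59% by log-rank. There is no inflation if transplant is unrelated to the factor; rejection is 13-16% if transplant is 20% v 50% by factor level.

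**The case against.** Several points on the other side are fair.

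- **Importance.** This is a secondary endpoint with no stated power, and the primary endpoint and sample size are untouched. That is true. But a stated rule puts a test that cannot handle censoring on the first-listed secondary endpoint.
- **Dependence on handling.** The worst power figures require dropping every non-progressor, which the plan does not say. Using all times costs less: 47% v 64%, or 63% v 69% with no competing events. This stands, so both readings are shown.
- **The 24-month cap.** The documents set no such cap. With 36 months' accrual and 24 months' minimum follow-up, at 30% each, log-rank power is 71%, against 24-25% and 54-56% for the t-tests. The loss shrinks but remains, as do the distortions when exit differs by arm.
- **Contrasts between arms.** No document gives exit rates by arm, and at 20% v 30% the inflation is mild. The 6/34 figure is one arm, transplant only, with progression status unknown.
- **What counts as false.** At 20% v 50% with equal progression hazards, a Gray-type test rejects in 21-28%, because progression is truly observed less often in one arm. Part of the chi-squared result is therefore a real difference in cumulative incidence. That does not rescue the t-test.
- **The log-rank benchmark.** Its 5-6% follows from assuming exit is independent of progression, and the three-monthly imaging grid is ignored. Downstaging can open the way to transplant, so independence is doubtful. This is why cumulative incidence belongs alongside.
- **Logistic regression.** The survival analysis already names one- and two-year time points and the power loss is small. It stays a minor point.

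**Conclusion.** The concern holds and should be fixed before analysis. By its wording the plan applies Student's t-test to a censored time-to-event endpoint, and no section gives an alternative or a censoring rule.

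With equal exit in both arms the harm is lost power only. At 30% each, the loss against log-rank is 64 − 47 = 17 percentage points if all times are used and 64 − 11 = 53 if non-progressors are dropped. With unequal exit, the t-test can hide a real delay or produce a difference where progression is the same; serious distortion needs a sizeable gap between arms, about 20% v 40% or more.

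The direction is the same under both sets of follow-up assumptions. The sizes rest on assumed exponential times, assumed progression and exit rates, and exit independent of progression.

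**What to change.** Replace the t-test for time to progression in Data and Statistics with wording such as:

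> Time to progression will be compared by log-rank test and cause-specific Cox model (hazard ratio, 95% CI). Patients without progression are censored at the last evaluable scan, or at transplant or death. Cumulative incidence of progression by arm, with transplant and death without progression as competing events, will be reported alongside (Gray's test), together with the incidence of those competing events by arm.

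State which test is the main one, because the two answer different questions when transplant or death differs by arm. Keep the t-test and chi-squared or Fisher's exact test for tumour diameter, response and downstaging.

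As a lesser change, replace logistic regression for factors affecting survival with a cause-specific Cox or Fine-Gray model that uses the same event and competing-event definitions as the primary analysis.

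The cost is analysis wording only: no new data, scans or patients.
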